8.1 Adverse Events and Serious Adverse Events

8.1.1 Definition of Adverse Events (AE)

Adverse event means any untoward medical occurrence associated with the use of an intervention in humans, whether or not considered intervention-related (21 CFR 312.32 (a)).

8.1.2 DUE TO THE NATURE OF THIS STUDY, THE RISK OF ADVERSE EVENTS IS EXTREMELY LOW. WE WILL REPORT ALL SERIOUS AES ACCORDING TO APPROPRIATE AUTHORITY (PCORI, IRB) USING STANDARD GUIDELINES AND REGULATIONS OUTLINED BELOW. DEFINITION OF SERIOUS ADVERSE EVENTS (SAE)

A SAE is any AE occurring at any dose that results in any of the following outcomes:

- Death
- Is life-threatening (places the participant, in the view of the site PI, at immediate risk of death from the AE as it occurred)
- Inpatient hospitalization or prolongation of existing hospitalization (hospitalization is defined as an inpatient admission, regardless of length of stay, even if hospitalized as a precautionary measure for continued observation)
- A permanent, persistent, or significant disability (substantial disruption of the ability to conduct normal life functions). A medically significant AE that may jeopardize the participant and may require medical or surgical intervention to prevent one of the outcomes listed in this definition

Events NOT considered to be **Serious** are:

- Hospitalization for treatment, which was elective or pre-planned, for a pre-existing condition that did not worsen
- Treatment on an emergency, outpatient basis for an event NOT fulfilling any of the definitions of serious given above and NOT resulting in hospital admission
- An event that, had it occurred in a more serious form, might have caused death
- A sign, symptom, or event that is noticeable but easily tolerated.
- An event does not significantly influence performance or prevent the participant from carrying on with their usual life activities.

8.1.2.1 Expectedness

Due to the nature of this study, there are no expected adverse events associated with this study.

8.2 Unanticipated Problems

8.2.1 Definition of Unanticipated Problems (UP)

Unanticipated problems, in general, are defined as any incident, experience, or outcome that meets all of the following criteria:

- Unexpected (in terms of nature, severity, or frequency) given (a) the research procedures that are described in the protocol-related documents, such as the IRB-approved research protocol and informed consent document; and (b) the characteristics of the participant population being studied;
- Related or possibly related to participation in the research (in this guidance document, possibly related means there is a reasonable possibility that the incident, experience, or outcome may have been caused by the procedures involved in the research); and
- Suggests that the research places participants or others at a greater risk of harm (including physical, psychological, economic, or social harm) than was previously known or recognized.

8.2.2 Unanticipated Problem Reporting

Any unanticipated problems will be reported to the appropriate authority (PCORI, IRB) and noted in the study database.

8.2.3 REPORTING UNANTICIPATED PROBLEMS TO PARTICIPANTS

Participants will be informed about unanticipated problems, and study-related results on an individual or aggregate level.

9 STATISTICAL CONSIDERATIONS

9.1 STATISTICAL HYPOTHESES

Specific Aim 1: Targeted participants for this Specific Aim are key informants (interviews) and all clinic personnel (surveys). The purpose of this Specific Aim is to identify and quantify clinic and contextual characteristics (e.g., readiness for change, physician attitudes, patient barriers) to inform strategy component selection and influence implementation effectiveness of lupus DA to be evaluated in Specific Aim 2. As such the statistical approach for this component of Aim 1 is largely descriptive and there are no formal statistical null and alternative hypotheses. Specific descriptive statistics are described in the table below and further details are provided in Section 9.4. Penetration will be assessed by evaluating the proportion of eligible patients reviewing the DA overall and in each site. Overall rates and 95% confidence intervals will be computed. Patient healthcare utilization outcomes (e.g., inpatient visits and ER/urgent care visits) will be assessed similarly.

Specific Aim 1 Data Collection and Analyses		
Data Type	Data Collection Type	Analytic Methods
Quantitative	Online & paper survey, Organizational readiness for implementing change (ORIC); Team Learning & Psychological Safety Survey (TLPSS)/ Baseline	Individual & practice level summary statistics Correlation
Qualitative	Semi-structured interviews with key informants/ Baseline	Within-case/clinic thematic analysis of CFIR domains Cross-case/clinic comparison

Specific Aim 2: Targeted patient participants for this Specific Aim are (1) age \geq 18 years with a diagnosis of lupus from participating clinics; for individual-level outcomes, initial analyses will focus on how clinic personnel and patient perceptions change over time. The statistical null hypothesis is the assumption that there is no change over time versus

the alternative that there is a change over time. For the analytic approach we will examine mean levels (total change) and quantify with means (or proportions, as appropriate) and 95% confidence intervals. We will also examine patterns of change (growth trajectories) while controlling for differences between clinics using multivariable models that account for repeated measures and clinic clustering of patients (i.e., generalized estimating equations (GEE) with robust standard errors). Additional analyses may examine by-group comparisons of clinics determined by clinical characteristics (e.g., geographic areas, clinic type, and patient diversity) observed in Specific Aim 1. Any such by-group analyses will be conducted separately. A primary independent variable of interest is the type of strategy used for implementation. Following completion of the study, each sites strategies will be evaluated and sites will be grouped accordingly. A covariate allowing for testing group differences will be included in the multivariable models to assess whether trajectories differ by implementation strategy.

The second component of our evaluation of Specific Aim 2 will use fuzzy set Qualitative Comparative Analysis (fsQCA) to assess effectiveness of implementation strategies for clinic-level outcomes. fsQCA is a case-oriented approach that examines relationships between conditions (similar to explanatory variables in regression models) and outcomes using set theory to answer the question: “what conditions, alone or in combination, are necessary or sufficient to produce an outcome?” For patient-physician communication analysis, question-asking, assertive responses, and expressions of concern, will be coded as patient participation; supportive talk and partnership building by provider will be coded as active physician communication. Further details are provided in Section 9.4.

Specific Aim 3: Targeted participants for this Specific Aim are the same key clinic informants from Specific Aim 1 and 2 patients per clinic from Specific Aim 2. Similar to Specific Aim 1, the analytic approach is largely descriptive and there are no formal statistical null and alternative hypotheses. Specific descriptive statistics are described in the table below. Further details are provided in Section 9.4.

Specific Aim 3 Data Collection and Analyses		
Data Type	Interview Content	Analytic Methods
Qualitative	Perceived challenges to long-term sustained use of the DA Understand the lessons learned	Within-case/clinic thematic analysis of CFIR domains Cross-case/clinic comparison

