8 STUDY ASSESSMENTS AND PROCEDURES

This study will be coordinated by the University of Alabama at Birmingham (UAB). All study visits and procedures will be performed at the United States, and at n = 16 sites. At least 35 participants are expected to be enrolled at each site. Enrollment will be competitive between sites.

Participants will be seen according to the details that follow:

Specific Aim 1: Clinic Personnel Survey/Semi Structured Interviews

This Specific Aim will: a) identify clinic staff and patient needs, and b) key contextual factors that inform targeted strategy selected influence implementation effectiveness, and sustainability. It will do so via two data collection efforts:

Clinic Personnel Survey

Up to 15 clinic personnel will be administered an online survey via Qualtrics® to assess their role in the clinic, clinic culture, and readiness to implement change. This will last between 20-25 minutes. Clinic personnel will be emailed a link to complete the survey. An automatic email will be generated in the Qualtrics® system and will go out to all non-responders every 24 hours for 5 days, or until the survey is completed.

Semi-Structured Interviews

Each site PI/ study coordinator will choose 6-8 key clinic staff that will be administered a 45-60 minute semi-structured interview either via phone or in person that will assess stakeholder needs and identify characteristics of the clinics (e.g., policy environment, physician, clinic, patient barriers) that influence DA adoption and choice of the implementation strategy. The interview protocol will be adapted to fit each time range and different key personnel. A link to the brief video animation introducing the decision-aid use and content along with the interview protocol and copy of the decision-aid will be emailed to clinic personnel prior to being interviewed. All interviews will be recorded and transcribed verbatim for accuracy.

Specific Aim 2: Implementation

Patient Baseline Visit

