For individual-level outcomes, initial analyses will focus on how clinic personnel and patient perceptions change over time. We will examine mean levels (total change) and patterns of change (growth trajectories) while controlling for differences between clinics using multivariable models that account for repeated measures and clinic clustering of patients (i.e., generalized estimating equations (GEE) with robust standard errors). The second component of our evaluation of **Aim 2** will use fuzzy set Qualitative Comparative Analysis (fsQCA) to assess the effectiveness of implementation strategies for clinic-level outcomes. fsQCA is a case-oriented approach that examines relationships between conditions (similar to explanatory variables in regression models) and outcomes using set theory to answer the question: “what conditions, alone or in combination, are necessary or sufficient to produce an outcome?”

For patient-physician communication analysis, question-asking, assertive responses, and expressions of concern will be coded as patient participation; supportive talk and partnership building by provider will be coded as active physician communication.

Specific Aim 3:

Similar to **Aim 1**, emergent theme analysis within each clinic will be initially conducted. These themes will focus identify the implementation lessons learned by the clinics, including and especially the implementation challenges faced by the clinic throughout the study, and their opinions of the opportunities and challenges to sustaining use of the DA once the study ends. These within-case themes also will be used to compare and contrast between clinics to identify common lessons learned and ideas for how to sustain the DA moving forward.

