9.4.7 Missing Data and Outliers

The rate of missing values will be evaluated on a variable-by-variable basis. Clinics and/or patients with extensive missing values will be deleted from all analyses. A clinic or patient with a missing value for any variable involved in a specific analysis will be excluded from that analysis only (case wise deletion). There are no plans for imputation of missing values. Theoretical assumptions for all statistical procedures will be evaluated (e.g., evaluation of normality, residual plots, and outlier evaluations). Any outliers will be inspected for data coding and entry errors and they will be corrected whenever appropriate. In the case of true outliers, sensitivity analyses with the specific values removed will be conducted in order to evaluate the robustness of the observed results.

In the event that there is insufficient (or excessive) variation in implementation strategies to create 2 clearly differentiable study groups, alternative definitions of the primary independent variable may be created (e.g., groups determined by number of strategies used or groups determined by percentage of staff trained).

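### Aim 2 GEE with robust standard errors on 16 clinics states no small-sample method; completed with uncorrected Wald tests and intervals, it would over-reject and under-cover

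*Combined protocol and SAP*

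**What the plan says.** Section 9.1 gives Aim 2 one formal null: "The statistical null hypothesis is the assumption that there is no change over time versus" the alternative of a change. It promises means or proportions with 95% confidence intervals, and growth trajectories analysed "using multivariable models that account for repeated measures and clinic clustering of patients (i.e., generalized estimating equations (GEE) with robust standard errors"). Section 9.4.2 repeats the method, again for "patterns of change (growth trajectories) while controlling for differences between clinics using multivariable models that account for repeated measures and clinic clustering of patients".

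Section 9.1 also states: "A primary independent variable of interest is the type of strategy used for implementation". Clinics are grouped by strategy once the study is complete, and "A covariate allowing for testing group differences will be included in the multivariable models to assess whether trajectories differ by implementation strategy". Section 9.4.7 anticipates two groups but allows other definitions if there is "insufficient (or excessive) variation in implementation strategies to create 2 clearly differentiable study groups".

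The number of clinics is 16 throughout. Section 8 sets a minimum of 35 patients per clinic and adds: "Enrollment will be competitive between sites". Section 9.4.7 provides that "Clinics and/or patients with extensive missing values will be deleted from all analyses".

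No part of Section 9 names a bias-corrected sandwich, a t or F reference, degrees of freedom, a score test, a permutation test or a working correlation. Section 9.4.1 names only the software: SAS, or R for specialty routines.

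**The concern.** The robust variance is justified by a large number of independent clusters. With clinic as the cluster there are 16, and recruiting towards 3,000 patients adds none. With few clusters the uncorrected sandwich is biased downwards and is itself variable, so referring a Wald statistic to the normal distribution rejects too often and gives intervals that are too short.

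This touches the only formal Aim 2 hypothesis and the variable that the plan singles out as of primary interest. Strategy is the more exposed of the two because it varies only between clinics, and an uneven split leaves few clinics in the smaller group.

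**Working it through.** **The plan's own figures.** The plan gives no type I error or power for these models, so there is nothing to reproduce directly. Section 9.2 gives only interval widths, which are not used here.

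**Inputs.** K = 16 clinics (Section 9.2). Patient times 0, 3 and 6 months and staff times 0, 6, 12 and 24 months (Section 2.2). Level 0.05, stated only in Section 9.4.4 and taken as two-sided. Assumed: clinic is the sandwich cluster, clinic sizes are equal (the ICC then cancels), and clinic means are normal. The strategy splits are also assumed, since the plan gives none.

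**Overall change, single-df contrast.** With equal sizes the GEE estimate is the mean of the 16 clinic-level changes. The uncorrected sandwich is (K−1)/K = 15/16 of the unbiased variance. Wald z therefore rejects when |t15| > 1.96 × √(15/16) = 1.898, which has probability 7.7%. Interval coverage is 100 − 7.7 = 92.3%.

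**Overall change, joint test of categorical time.** The Wald chi-square on q df rejects when F(q, K−q) > χ²(q, 0.95) × (K−q)/(qK).
- Patients, q = 2: 5.991 × 14/32 = 2.621 on F(2,14), giving 10.8%.
- Staff, q = 3: 7.815 × 13/48 = 2.116 on F(3,13), giving 14.7%.

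**Strategy, two groups, no other clinic-level covariate.** The uncorrected variance is Σe²/n² in each group, summed. At 8:8, Wald z rejects when |t14| > 1.96 × √(7/8) = 1.833, giving 8.8%. Unequal splits need integration over the two chi-square variances, checked by simulation.

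| Split | Wald z, uncorrected | Robust score test | Kauermann-Carroll, data-driven Satterthwaite df |
|---|---|---|---|
| 8:8 | 8.8% | 5.4% | 4.8% |
| 5:11 | 10.7% | 4.6% | 5.2% |
| 4:12 | 12.8% | 3.4% | 5.7% |
| 3:13 | 16.9% | 0.5% | 6.9% |

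Wald interval coverage from 8:8 to 4:12 is therefore about 91% down to 87%. Using t14 without correcting the variance leaves about 6.5% at 8:8 and 10% at 4:12. For overall change the robust score test rejects when |t15| > √(1.96² × 15/(16 − 1.96²)) = 2.177, giving 4.6%.

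**Check on fitted models.** GEE fits with an independence working correlation and clinic clusters (35 patients per clinic, two visits, about 7,900 data sets per split) gave 7.9–8.1% overall, 9.1% at 8:8 and 12.3% at 4:12. Monte Carlo error is 0.3–0.4 points.

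**Departures from the base case, Wald z.**
- Uneven enrolment, assumed sizes of 35 to 460 totalling 3,000, independence working correlation: 10.4% overall and 13.0–18.8% for strategy (8:8 to 4:12).
- Uneven enrolment with an exchangeable working correlation at the true ICC, under assumed lognormal size patterns: 8.6–13.3% for strategy, close to the equal-size range.
- One further binary clinic-level covariate: about 11%, 12.6% and 14.4% at 8:8, 5:11 and 4:12.
- Two clinics deleted, leaving 14: 8.1% overall and 9.5% for strategy at 7:7.

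**The case against.** The strongest reply is that the plan never commits to a Wald z test. A reader might infer that Aim 2 will run at 7.7–12.8% error; the documents do not support that. They leave the test form open, and a robust score test would be at 4.6% overall and 3.4–5.4% for strategy from 8:8 to 4:12. This stands, and it makes every error rate above conditional. It does not close the gap: the plan also promises 95% confidence intervals, and Wald-type intervals from an uncorrected sandwich under-cover whichever test accompanies them.

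The cluster unit is also an inference. Controlling for clinic differences could mean clinic fixed effects with patients as clusters, and the problem would then take another form. Clinic as cluster is the natural reading of the text, but the text mentions clustering of patients only and says nothing about staff surveys.

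The strategy splits are assumptions too. Section 6.3 expects 16 different approaches, and the groups are formed afterwards. With equal sizes, however, no two-group split brings the uncorrected Wald z error below 8.8%.

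A reader might go further and conclude that the strategy findings as a whole are unsound for this reason. That goes too far. The study is observational, sites choose their own tailored activities (Section 6.1), and confounding would remain after any variance correction. No decision rule rests on the strategy p-value, and the qualitative comparative analysis of clinic-level outcomes is unaffected. Nor does uneven enrolment always worsen the error materially: it does so mainly under an independence working correlation.

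**Conclusion.** The omission is real and should be fixed. What the documents establish is that a large-cluster method is specified for 16 clinics with no test form, reference distribution or small-sample correction. The excess error and under-coverage calculated here follow only if uncorrected Wald methods are used with clinic as the cluster, equal sizes, and (for strategy) a two-group split between 8:8 and 4:12 with no other clinic-level covariate. On that footing a non-existent strategy difference would be declared about 1.8 to 2.6 times as often as 5% implies (8.8/5 to 12.8/5). Confidence is high in the omission and in the conditional arithmetic. It does not extend to any claim about the error rate the study will actually have.

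**What to change.** In Sections 9.1 and 9.4.2, state that all Aim 2 GEE tests and confidence intervals, for patients and for staff, use:
- clinic as the cluster, with a named working correlation;
- the Kauermann-Carroll bias-corrected sandwich variance;
- a t reference with data-driven Satterthwaite degrees of freedom for single contrasts;
- a small-sample F with clinic-based denominator degrees of freedom for joint tests of time (K−q, so 14 for patients and 13 for staff if all 16 clinics are analysed and there is no clinic-level covariate).

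Apply the same rule to the clinic-level subgroup contrasts in Section 9.4.6, which rely on the approaches already described.

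If the smaller strategy group has three clinics or fewer, even the corrected test runs at about 6.9% (3:13). In that case report the strategy contrast as descriptive, or add a permutation test on clinic-mean change as a sensitivity analysis. That test weights clinics equally, so with uneven enrolment it estimates a different quantity from the patient-weighted model and should not replace it.

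The cost is wording and a software option; Section 9.4.1 already allows R routines, and no new data are needed. With equal sizes, intervals widen against uncorrected Wald z by about 12% for overall change (√(16/15) × 2.131/1.96 = 1.12), and for strategy by about 18%, 30% and 46% at 8:8, 5:11 and 4:12.

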9.2 Sample Size Determination

A power analysis for the quantitative portion of Specific Aim 2 was conducted using the following assumptions: (1) 16 clinics and (2) an intraclass correlation coefficient of 0.05. This provided us with a total confidence interval width of 5.3% for 10% of the total clinic population that is administered the lupus DA to a width of 8.1% , if 40% patients are administered the lupus DA. For outcomes on a 5-point Likert scale, the corresponding 95% CI widths for standard deviation of 0.5 and 2.0 on the mean score is estimated to be 0.09 vs. 0.35, respectively. For individual-level outcomes measured as a rate (e.g., # visits/1,000) or as means (e.g., Likert-scale), we anticipate small margins of error. A minimum number of proposed sites (n=16) are needed to comprehensively assess how different implementation strategies are influenced by and interact with different contextual conditions (different geographic areas, clinic type, and patient diversity) to affect implementation effectiveness, and thus, determine the generalizability of the study findings. However, given the proven effectiveness of the DA (original PCORI study), and in the spirit of dissemination and implementation research, we will continue to recruit to our proposed maximum sample size target of 3,000.

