9.3 Populations for Analyses

The analysis population for each Specific Aim is below:

Specific Aim 1

- Key clinic personnel who complete the semi-structured in depth phone interview (6-8 staff per clinic)
- Clinic personnel who complete the online clinic personnel survey (all staff, up to 15 per clinic)
- Using administrative records, sites will report the total number of patients viewing the DA and the total number of patient visits during the active study time frame.

Specific Aim 2

- All enrolled participants who complete the baseline visit, as well as those who complete the three and six month follow-up questionnaires
- Clinic personnel who complete the online surveys

Specific Aim 3

- Key clinic personnel from Aim 1+ 2 patients per site who complete the post-study semi-structured in depth phone interview. (6-8 key clinic personnel + 2 patients per site)
-

The protocol population will be all participants who attend all study visits and complete the trial.

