9.4.4 Baseline Descriptive Statistics

Clinical characteristics and patient demographics will be collected. Descriptive statistics will be reported using means and standard deviations (or medians and quartiles) for continuous-type data and using counts and proportions for categorical-type data. For any by-group comparisons, the two-sample t-test (or Wilcoxon Rank Sum test, as appropriate)

will be used to evaluate continuous-type data. The chi-square test of independence (or Fisher's exact test, as appropriate) will be used to evaluate categorical-type data. Statistical significance will be evaluated at a 0.05 level. Descriptive statistics will be presented overall and by groups defined by implementation strategy.

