9.4.6 Sub-Group Analyses

We are planning the following subgroup analyses, if enough data are available. The analysis approaches are described above.

- Clinics with vs. without prior experience with DA,
- Setting, private vs. academic,
- Location, urban vs. suburban,
- Type of clinic, general rheumatology clinic vs. lupus clinic vs. rheumatology/renal hybrid clinic,
- By the language of decision-aid used English vs. Spanish,
- Patient characteristics including the biological variables (age group, sex, race/ethnicity), and
- The proportion of patients with Medicaid/Medicare vs. private insurance
- By presence of renal disease
- By level of education
- By insurance mix (>30% private)

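### The two-sample tests named for by-group comparisons ignore clinic clustering when the groups are made of whole clinics, and no test of difference is specified for the listed subgroups

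*Combined protocol and SAP*

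**What the plan says.** Section 9.4.4 (Baseline Descriptive Statistics) gives the testing rule: "For any by-group comparisons, the two-sample t-test", with Wilcoxon as the alternative, and chi-square or Fisher's exact test for categorical data. It adds "Statistical significance will be evaluated at a 0.05 level". The same paragraph ends by presenting the descriptive statistics overall and by implementation-strategy group. No clustering adjustment is mentioned there.

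Section 9.1 (Aim 2) says that sites are grouped by strategy after the study, so strategy is a clinic-level factor. It puts a strategy covariate into a GEE with robust standard errors that allows for repeated measures and clinic clustering. For optional comparisons of clinics by geography, clinic type or patient diversity it says only: "Any such by-group analyses will be conducted separately". Section 9.4.2 repeats the GEE without a subgroup term.

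Section 9.4.6 says "We are planning the following subgroup analyses, if enough data are available", gives ten bullets, and refers back for the method without naming a section. Section 9.2 justifies the number of sites by the wish to learn how strategies interact with clinic context.

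**The concern.** There are two gaps.

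First, patients in one clinic resemble each other. When the groups being compared are made of whole clinics, the information about the group difference comes mainly from 16 clinics rather than from hundreds or thousands of patients. An ordinary two-sample test treats every patient as independent, so its p-value is too small. Baseline tables by strategy would then tend to show imbalances that are only clinic-to-clinic variation, and these could drive covariate choice or the interpretation of the strategy comparison.

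Second, a statement that a context or patient group responds differently needs an estimate of the difference, with its uncertainty. The plan names none for its listed subgroups, although interaction with context is a stated reason for having 16 sites. An analyst could follow Section 9.4.4, fit the GEE within each group, or add a term to the full GEE, and could claim in each case to comply.

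**Working it through.** **Inputs**

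| Input | Value | Source |
|---|---|---|
| Clinics and intraclass correlation (ICC) | "1) 16 clinics and (2) an intraclass correlation coefficient of 0.05" | Section 9.2 |
| Minimum per clinic, m | 35: "At least 35 participants are expected to be enrolled at each site" | Section 8 |
| Maximum, if spread evenly | 3,000/16 = 187.5: "we will continue to recruit to our proposed maximum sample size target of 3,000" | Section 9.2 |
| Nominal level | 0.05, taken as two-sided | Section 9.4.4; sidedness is an assumption |

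**The plan's own figures.** The plan gives no power, effect size or error rate for any by-group test. Its only precision figures are the confidence-interval widths in Section 9.2: 5.3% at a proportion of 10% and 8.1% at 40%. Section 9.2 states no sample size for them. Taking 16 × 35 = 560 patients and ICC 0.05, the effective sample size is 560/2.70 = 207.4. The widths are then 2 × 1.96 × √(0.1 × 0.9/207.4) = 8.2% and 2 × 1.96 × √(0.4 × 0.6/207.4) = 13.3%. The stated widths are not reproduced. That is a separate matter; only the number of clinics and the ICC are used below.

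**Which factors are clinic-level.** Strategy, prior experience with the decision aid, setting, location and clinic type are. The two insurance bullets that speak of a proportion or a mix may be. Language, age, sex, race/ethnicity, renal disease and education vary within clinics.

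**Error of an unclustered test on a clinic-level factor.** The variance of the group difference is larger than the test assumes by the design effect DE = 1 + (m − 1) × ICC. The true error is 2 × [1 − Φ(1.96/√DE)].

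| m | ICC | DE | 1.96/√DE | True type I error |
|---|---|---|---|---|
| 35 | 0.01 | 1.34 | 1.69 | 9.0% |
| 35 | 0.05 | 2.70 | 1.19 | 23.3% |
| 35 | 0.10 | 4.40 | 0.93 | 35.0% |
| 187.5 | 0.05 | 10.325 | 0.61 | 54.2% |

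Simulation with 16 clinics, ICC 0.05 and 5,000 runs per setting agrees. At 35 per clinic the error is 23.4% for an 8-versus-8 split of clinics and 22.9% for 12 versus 4. At 187 per clinic it is 53.5% and 53.1%. A t-test on the 16 clinic means, in the same four settings, gives 4.7% to 5.5%.

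**Patient-level factors.** For a factor split evenly within each clinic, the simulated error of the unclustered test at 35 per clinic is 4.9%. There is no inflation. A factor whose mix differs between clinics lies in between.

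**Test of difference.** The places to which Section 9.4.6 could refer are:

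- Section 9.1: optional comparisons of clinics, done separately, with no test named.
- Sections 9.1 and 9.4.2: a clustered GEE whose only group term is strategy.
- Section 9.4.2, Aim 1: t-tests and ANOVAs on clinic survey scores.
- Section 9.4.4: two-sample tests at baseline.

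None gives a subgroup-by-time term. If the GEE were run once per group and both groups had the same true effect and the same power p, exactly one would be significant with probability 2p(1 − p). That is 50% at p = 0.5, 32% at 0.8 and 18% at 0.9. The documents state no power, so this is a range and not a forecast.

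**Multiplicity.** Ten valid, independent tests at 0.05 give at least one false positive with probability 1 − 0.95^10 = 40%. If age, sex and race/ethnicity are counted separately there are twelve, and the figure is 46%. No multiplicity rule is stated for these analyses.

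**The case against.** The strongest reply is that the two-sample tests sit in a section on baseline description, while the Aim 2 outcome method, stated twice, is a GEE that handles clustering. A reader might infer that outcome subgroups will be analysed with unclustered tests. The documents do not say so: Section 9.4.6 names no section, and the GEE is at least as natural a referent. Clinic type there has three levels, which a two-sample test does not fit.

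A reader might also infer that separate conduct means one model per group with the p-values compared. The sentence could equally mean apart from the main models, or one characteristic at a time. It is optional, and it covers clinic characteristics only. fsQCA also addresses combinations of clinic conditions.

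All of this stands, and it confines the point. It does not remove it. Even as a baseline rule, Section 9.4.4 attaches a 0.05 level to patient-level tests and presents strategy groups in the same paragraph; those groups consist of whole sites. On any reading of the sentence in Section 9.1, no test of difference is named for the listed factors. fsQCA looks for necessary and sufficient conditions for clinic-level outcomes; it does not estimate a subgroup difference with an interval.

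**Conclusion.** The point holds in two parts.

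1. Used on clinic-level groups, the Section 9.4.4 tests have a true error of about 23% at the minimum enrolment and about 54% at the maximum, against a nominal 5%. This assumes equal clinic sizes, two-sided tests, and that the ICC of 0.05, stated for the Aim 2 power analysis, also fits the variables tested. For baseline variables that is an assumption; at 35 per clinic the range is 9% to 35% for ICC 0.01 to 0.10. Patient-level factors balanced within clinics are outside this part.
2. For the ten subgroup bullets the plan specifies no test of difference and no multiplicity rule.

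The strategy comparison of Aim 2 outcomes is correctly placed in the clustered GEE. It would also be wrong to infer that most reported subgroup differences will be false: a type I error rate is not the share of observed differences that are false, and the method for outcome subgroups is open, not stated to be unclustered.

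**What to change.** Replace the Section 9.1 sentence on separate conduct, and the reference back in Section 9.4.6, with:

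> Each subgroup factor is examined in the full-sample GEE through factor and factor-by-time terms, clustered by clinic, with a small-sample correction to the robust standard errors for 16 clusters (or, for clinic-level factors, an analysis of clinic-level summaries). The interaction estimate and its 95% CI are reported. Within-subgroup results are shown only beside it. These analyses are exploratory.

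The small-sample correction is needed because uncorrected robust standard errors tend to be too small with so few clusters.

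In Section 9.4.4, limit the two-sample tests to groups that vary within clinics. For strategy, setting, location, clinic type and prior experience with the decision aid, give description without p-values, or use cluster-adjusted tests.

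The cost is analysis-plan wording and a few added terms in a model already planned. Data collection does not change. The downside is that the interaction intervals will be wide with 16 clinics and will look less favourable than unclustered or within-group results.
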